Scenario #2: At the time of disease progression while being treated with a CDK4/6 inhibitor (ribociclib **or** palbociclib **or** abemaciclib)+ AI, tamoxifen or fulvestrant

In scenario #1, the study will provide patients with ribociclib + letrozole, but patients will not be randomized until they demonstrate objective evidence of disease progression on treatment. If the patient has previously received letrozole, an alternative AI can be prescribed but will not be provided by the study, i.e. administered as standard of care (ribociclib and letrozole will still be provided by the study). Patients are allowed to have received 4 consecutive weeks of an aromatase inhibitor prior to protocol registration for scenario 1. In scenario #2, patients will be randomized after registration.

At randomization, patients will be assigned to one of the two arms in a 1:1 ratio: 1) Fulvestrant (or exemestane) + ribociclib **or** 2) Fulvestrant (or exemestane) + placebo. Fulvestrant will be given as a 500 mg dose intramuscularly (IM) every 2 weeks for 3 times (loading dose) and then every 4 weeks, as per standard of care. Exemestane will be given as 25 mg orally daily, as per standard of care. The investigational drug ribociclib will be given as 600 mg daily, 3 weeks on/1 week off. Placebo will be administered on the same schedule. For all patients, ribociclib/placebo will be supplied by the study. Fulvestrant or exemestane will be given, as standard of care.

If patient received prior fulvestrant, exemestane must be the hormone therapy backbone in the randomization. If patient received prior exemestane, fulvestrant must be the hormone therapy backbone in the randomization. If neither has been administered, selection of fulvestrant or exemestane in the randomization will be per investigator discretion.

Accrual Target: N= 120 randomized, evaluable patients. Patients will be accrued from 11 academic medical centers in the US, with a goal of completing accrual in two years.

We will ensure that neither registration scenario contains > 60% (N=80) of total study accrual.

Patients will receive treatment on study until disease progression, unacceptable toxicity, or death or withdrawal from study based on patient choice or treating physician's discretion. Every effort will be made to follow patients for primary and secondary outcomes regardless of treatment discontinuation for any reason. Crossover is not built into the study.

Evaluations

Safety Assessment:

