1.2 OBJECTIVES

1.2.1 Primary Objectives:

1. To evaluate the progression-free survival (PFS) of fulvestrant or exemestane with or without ribociclib after progression on anti-estrogen therapy plus cyclin-dependent kinase 4/6 inhibitor in patients with hormone receptor positive (HR+), HER2- breast cancer.

- **Endpoint: PFS.** Defined as the interval from time of randomization until objective disease progression (local assessment) or death from any cause. Kaplan-Meier estimates will be used to calculate medians and 95% confidence intervals for PFS. A one-sided log-rank test will be used to test for a difference in PFS between the two arms.

1.2.2 Secondary/Exploratory Objectives:

1. To assess the Overall Response Rate (ORR = complete + partial response rate) and Clinical Benefit Rate (CBR= ORR + stable disease rate at ≥ 24 weeks of follow up) in the study population in both arms of the trial, post-randomization.

- **Endpoints: ORR, CBR.** Evaluation of disease will be made according to RECIST criteria (version 1.1) in patients with measurable disease. As this study will enroll patients with measurable and un-measurable disease as defined by RECIST v1.1, ORR will only be assessed in evaluable patients. CBR will also be determined. Patients with non-measurable disease only can be categorized as ‘complete response’, ‘non-complete response’, ‘non-progressive disease’, or ‘progressive disease’, but are sometimes not evaluable. (Section 11.1.4.2: Evaluation of Non-Target Lesions).
 - **Duration of overall response:** The duration of overall response is measured as the time interval from when measurement criteria are met for complete or partial response (whichever is first recorded) until the first date that recurrent or progressive disease is objectively documented
2. For patients in registration scenario #1, to assess the PFS, ORR, CBR, and safety of ribociclib with an aromatase inhibitor in patients with metastatic or unresectable HR+ HER2- breast cancer. This analysis will be based on data collected in the pre-randomization component of the trial for patients registered under scenario #1. There is no comparator arm for this component of the trial, but it will add to the available clinical safety and efficacy data with ribociclib + AI in this population.

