Patients will be potentially eligible and registered for the trial at 2 time periods: either a) no prior CDK4/6 plus an aromatase inhibitor - or - b) patients who have progressed on palbociclib or ribociclib or abemaciclib plus an aromatase inhibitor or tamoxifen or fulvestrant. Patients not previously treated with a CDK4/6 inhibitor will be provided with ribociclib with letrozole by the study supplier (Novartis), after registration. If and when these patients demonstrate evidence of disease progression on this combination, and if they continue to meet the other eligibility criteria, they will be randomized to receive either fulvestrant (or exemestane) with ribociclib or fulvestrant (or exemestane) with placebo. Eligible patients who register after disease progression on ribociclib or palbociclib or abemaciclib (received either as part of a clinical trial or as standard of care) will be immediately randomized to receive fulvestrant with ribociclib or placebo.

2.7 Biomarker Studies:

While most patients with ER-positive, HER2-negative metastatic breast cancer do appear to obtain a clinical benefit from CDK4/6 inhibition (either partial response or prolonged stable disease), validated biomarkers to predict which patients would benefit the most from CDK4/6 inhibition and to predict the small group of patients who may not benefit at all from CDK4/6 inhibition have not yet been identified. We propose to evaluate tissue biomarkers on archived formalin-fixed paraffin-embedded (FFPE) tissue, available from diagnostic biopsy procedures, and to perform optional biopsies prior to treatment, at time of disease progression (in the case of patients registered under scenario # 1), and at progression on fulvestrant (or exemestane) + ribociclib/placebo. We also plan to collect peripheral blood specimens (serum and plasma) for the purposes of future blood based biomarker studies. This serum and plasma will be stored and processed at the local institution and then requested to be shipped to CUMC when requested. Further details are available in the biomarkers section of this protocol (Section 9).

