- Scenario 2: the patient must have received an aromatase inhibitor (letrozole, arimidex, exemestane) or tamoxifen or fulvestrant plus palbociclib as standard of care **or** received a CDK4/6 inhibitor (palbociclib or ribociclib or abemaciclib), **and** demonstrated evidence of disease progression. If the patient was enrolled in a randomized clinical trial involving ribociclib or abemaciclib or palbociclib (such as the MONALEESA or PALOMA series of trials), then it **must** be known after study discontinuation and unblinding that the patient received the investigational drug and not placebo. Ribociclib or abemaciclib or palbociclib can also be given as standard of care. Documentation of progression and duration of response on aromatase inhibitor or tamoxifen plus CDK 4/6 inhibitor should be provided whenever possible. If patient received prior fulvestrant, exemestane must be the hormone therapy backbone in the randomization. If patient received prior exemestane, fulvestrant

must be the hormone therapy backbone in the randomization. If neither has been administered, selection of fulvestrant or exemestane in the randomization will be per investigator discretion.

- Adequate baseline laboratory studies (hematologic and chemistry), including the following parameters:
 - Absolute neutrophil count ≥ 1500 per microliter, Platelets $\geq 75,000$ per microliter, Hemoglobin level ≥ 8.0 gm/dL on screening complete blood count
 - Potassium and total calcium (corrected only in the case of hypoalbuminemia) within normal limits of the local laboratory (Screening values can be rechecked after electrolyte repletion and before the first dose of study medication, if necessary.)
 - Serum creatinine level ≤ 1.5 mg/dL **or** estimated glomerular filtration rate ≥ 50 mL/min.
 - In absence of liver metastases, alanine aminotransferase (ALT) and aspartate aminotransferase (AST) should be below $2.5 \times$ the upper limit of normal (ULN). If the patient has liver metastases, ALT and AST should be $< 5 \times$ ULN.
 - Total bilirubin $\leq 1.5 \times$ ULN. (In patients with well documented Gilbert's Syndrome, total bilirubin $\leq 3 \times$ ULN with direct bilirubin within normal range.)
 - INR ≤ 1.5
- (a) Written informed consent and HIPAA authorization obtained from the subject/legal representative prior to performing any protocol-related procedures;

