(b) Subjects must be willing and able to comply with scheduled visits, treatment schedule, laboratory testing, and other requirements of the study
- Must be able to swallow ribociclib and oral aromatase inhibitor, such as letrozole or exemestane.

3.2 Exclusion Criteria:

A subject **who meets any of the following criteria is ineligible** for the study:

1. Patient has a known hypersensitivity to any of the excipients of ribociclib, aromatase inhibitors (such as letrozole) or fulvestrant.
2. **Active** central nervous system (CNS) disease. History of CNS metastases or cord compression is allowable if the patient has been clinically stable for at least 4 weeks since completion of definitive treatment and is off systemic steroids. In the case of brain metastases, the patient must have stable or improved imaging at least 4 weeks after completion of definitive treatment. If there is evidence of active leptomeningeal disease, the patient is ineligible.
3. Identified as having visceral crisis, lymphangitic spread, or leptomeningeal carcinomatosis. Visceral crisis is not the mere presence of visceral metastases but implies severe organ dysfunction as assessed by symptoms and signs, laboratory studies, and rapid progression of the disease.
4. Received more than 1 prior systemic chemotherapy in the unresectable or metastatic setting. If the patient received 1 prior systemic chemotherapy, the patient is eligible. Having received prior therapies for breast cancer (such as everolimus or experimental agents) does not affect eligibility for this study.
5. Completion of major surgery, chemotherapy, targeted therapy (such as everolimus or experimental agents) or radiation within 14 days prior to starting investigational drug **or** has not recovered from major side effects. There is no required washout period from completion of prior anti-estrogen therapy (either scenario) or prior CDK 4/6 inhibitor (if scenario 2) to initiation of ribociclib/placebo and anti-estrogen on trial.

6. Residual acute toxic effects of prior anti-cancer therapy that have not resolved to CTCAE v.4 Grade \leq 1. Exception to this criterion: patients with grade 1 taxane-induced neuropathy, any grade of alopecia, amenorrhea or other toxicities not considered a safety risk for the patient as per investigator's discretion, are allowed to enter the study.

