4. REGISTRATION PROCEDURES

***** Please see Appendix F for Guidelines for Affiliate Institutions for Registration and Data Reporting Requirements.**

CUMC Research Participant Registration (CUMC Subjects ONLY)

Confirm eligibility as defined in Section 3.

Obtain informed consent, by following procedures defined in section entitled Informed Consent Procedures, along with applicable institutional policies and federal regulations.

Only Investigators/Research personnel properly trained and delegated to consent subjects for this protocol will participate in the consenting process. Furthermore, properly delegated/trained Physician Investigators (i.e., MD, MD PhD) are required to sign/verify a protocol specific Eligibility Checklist for each subject enrolled on the study, in addition to providing the relevant source documentation to confirm subject eligibility.

All participants must be centrally registered through the Central Registration Office within Herbert Irving Comprehensive Cancer Center at CUMC prior to initiation of study treatment.

Registration hours are available Monday through Friday from 9:00am – 5:00pm EST (excluding holidays and weekends). Same day patient registrations (and after hour registrations) will be accommodated on a case-by-case basis provided that the study team has expressed all time sensitive registration concerns/cases in a timely manner to the Central Registration Office.

CPDM Central Registration Procedures:

Within 48 hours of obtaining consent (excluding holidays and weekends), a completed/signed IRB approved informed consent HIPAA form, and demographics forms must be submitted to the CPDM Central Registration Office via an email to [contact] or fax to [contact], with the subject line “[**PROTOCOL# AAAP9506 Pending Subject Registration Request (PHI)**”. Upon receipt, applicable subject information as well as a “pending eligibility” status will be entered into HICCC’s

institutional database. This status will remain until further source documentation is made available to confirm overall patient eligibility. Required materials for all pending registration submissions are as follows:

- Completed/signed IRB approved/stamped Informed Consent Forms, including additional study ICFs (i.e. tissue, DNA, etc.) as applicable
- The completed/signed IRB approved HIPAA Authorization form
- Completed/signed CPDM ICF checklist
- Completed/signed HICCC personal census form
- Completed/signed CPDM Demographics Note to File

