6. TREATMENT PLAN

6.1 Study Design:

This is a phase II, multi-center, randomized, double-blinded, placebo-controlled trial to evaluate fulvestrant (or exemestane) +/- ribociclib (1:1 randomization) in patients with HR+HER2- breast cancer who have previously progressed on an aromatase inhibitor, fulvestrant, or tamoxifen plus CDK4/6 inhibitor (either palbociclib or ribociclib or abemaciclib). There is no crossover. If patient received prior fulvestrant, exemestane must be the hormone therapy backbone in the randomization. If patient received prior exemestane, fulvestrant must be the hormone therapy backbone in the randomization. If neither has been administered, selection of hormone therapy in the randomization will be per investigator discretion. Progression free survival is the primary endpoint. The trial will determine whether there is clinical benefit to continuing CDK4/6 inhibition beyond progression.

Registration:

Patients can be screened and registered at two different time points:

Registration Scenario #1: Before receiving any CDK4/6 inhibitor **or**

Scenario #2: At the time of disease progression while being treated with a CDK4/6 inhibitor (ribociclib or palbociclib or abemaciclib) + endocrine therapy

Registration Scenario #1: If the patient has never received a CDK 4/6 inhibitor previously, the patient is eligible for the trial. If the patient has not received letrozole previously, we are recommending that letrozole and ribociclib be administered (supplied by the study). If the patient has, for instance, progressed on adjuvant letrozole, the patient can receive anastrozole plus ribociclib prior to randomization (but anastrozole will need to be supplied per standard of care/insurance).

Patients are allowed to have received 4 consecutive weeks of an aromatase inhibitor prior to protocol

[figure not shown]
registration for scenario 1. Other studies have allowed this, including CALGB 40503 (letrozole +/- bevacizumab).

Registration Scenario #2: If a patient is on a clinical trial with ribociclib or abemaciclib or palbociclib (such as MONALEESA-2 or PALOMA-2) or abemaciclib and is clearly getting the CDK4/6 inhibitor (after unblinding) **or** if a patient is abemaciclib or ribociclib or palbociclib as standard of care, the patient **is eligible** for this study upon progression on the combination. Any aromatase inhibitor, fulvestrant, or tamoxifen along with a CDK4/6 inhibitor is allowed. (scenario #2).

Randomization:

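### The Scenario 2 criterion in Section 3.1 is looser than the synopsis and Section 6.1: it does not tie disease progression to the CDK4/6 inhibitor

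*Combined protocol and SAP*

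**What the plan says.** Most of the protocol describes one population. The synopsis defines Scenario 2 as registration "At the time of disease progression while being treated with a CDK4/6 inhibitor" and Section 6.1 repeats this. Section 6.1 then says that a patient given the inhibitor in a trial or as standard care is eligible "for this study upon progression on the combination". Section 2.6 speaks of "patients who have progressed on palbociclib or ribociclib or abemaciclib plus an aromatase inhibitor or tamoxifen or fulvestrant". The primary objective in Section 1.2.1 concerns treatment "after progression on anti-estrogen therapy plus cyclin-dependent kinase 4/6 inhibitor in patients with hormone receptor positive" disease, and Section 13.1 likewise describes patients who previously progressed on endocrine therapy plus a CDK4/6 inhibitor.

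The Scenario 2 criterion in Section 3.1 is worded differently. The patient must have received endocrine therapy plus palbociclib, or have received any of the three CDK4/6 inhibitors, and must have "demonstrated evidence of disease progression". It does not name the treatment on which progression occurred. On records it says: "Documentation of progression and duration of response on aromatase inhibitor or tamoxifen plus CDK 4/6 inhibitor should be provided whenever possible".

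In Section 3.2, the exclusion on prior chemotherapy adds: "Having received prior therapies for breast cancer (such as everolimus or experimental agents) does not affect eligibility for this study". The next exclusion requires no washout after a prior CDK4/6 inhibitor, and no maximum interval is given.

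The synopsis refers to Section 3 for the complete criteria. Section 4 instructs staff: "Confirm eligibility as defined in Section 3".

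**The concern.** The trial asks whether continuing CDK4/6 inhibition helps once the disease has progressed on it. That needs patients whose disease grew while they were taking the class. A patient who stopped the inhibitor for toxicity, and whose disease grew later off drug or on another regimen, has not been shown to be resistant. The protocol's own background makes the distinction: Section 2.6 describes xenograft tumours that regrew after drug withdrawal and were as sensitive as before on re-treatment.

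If such patients enter in any number, a positive PFS result could come partly from re-treating still-sensitive disease. Nothing in Section 13.1 would separate the two explanations. Its sensitivity analyses address incomplete lesion measurements, discontinuation and interval censoring, and its one named subgroup is fulvestrant versus exemestane.

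**Working it through.** **Step 1: the texts side by side**

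| Place | Exposure | Progression |
|---|---|---|
| Synopsis and Section 6.1, Scenario 2 definition | CDK4/6 inhibitor plus endocrine therapy | While being treated |
| Section 6.1, eligibility sentence | Same | On the combination |
| Sections 1.2.1, 2.6 and 13.1 | Same | On, or after progression on, the combination |
| Section 3.1, Scenario 2 | Endocrine therapy plus palbociclib, or a CDK4/6 inhibitor received | Demonstrated; treatment not named |

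Take a patient who received a CDK4/6 inhibitor, stopped for toxicity and progressed later on another therapy. This patient fails the first three rows. Under a literal reading of the fourth, the patient passes, and nothing in Section 3.2 excludes them.

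**Step 2: how much of the trial uses this criterion**

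The pre-randomisation table in Section 6.2 shows 27 Scenario 1 patients treated and says that scenario is closed. Even if all 27 were randomised, 120 − 27 = 93 of the 120 planned patients (77.5%) would have to enter through Scenario 2.

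**Step 3: the plan's design figure**

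Inputs from Section 13.1 are medians of 3.8 and 6.5 months, one-sided alpha 0.025 and 80% power; allocation is 1:1. Section 13.1 also calls the effect 3 months, although 6.5 − 3.8 = 2.7. I use the two medians.

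- HR = 3.8/6.5 = 0.585, ln HR = −0.537.
- Events (Schoenfeld) = 4(1.96 + 0.8416)²/(0.537)² = 31.4/0.288 ≈ 109. Freedman's formula gives 115.
- With 24 months of uniform accrual, exponential PFS, no loss and an assumed 12 months of further follow-up, 120 patients yield about 112 events and 81% power. With the 30 months in Section 6.5.1 (survival follow-up; no PFS cut-off is stated), they yield about 119 events and 83%.

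The stated 80% is therefore reproduced, given adequate follow-up. The eligibility wording does not alter it.

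**Step 4: illustration of what mixing could do**

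The documents give no share of still-sensitive patients, so the share f is an assumption. Let the HR be 1.0 in patients who truly progressed on the class and 0.42 in the rest. The 0.42 is the palbociclib plus fulvestrant result quoted in Section 2.3, from a trial whose patients were all CDK4/6-naive. Approximations: pooled HR = 0.42^f; mean of Z = √(109/4) × |ln pooled HR|, where √(109/4) = 5.22.

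| f | Pooled HR | Mean of Z | P(Z > 1.96) |
|---|---|---|---|
| 0 | 1.000 | 0 | 2.5% |
| 10% | 0.917 | 0.45 | 6.6% |
| 20% | 0.841 | 0.91 | 14.6% |

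A log-rank simulation without the pooling approximation (120 patients, 24 months accrual, 6 months follow-up, 6,000 runs per setting) gave 2.7%, 7.4% and 16.3%.

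**Step 5: a weaker effect in previously exposed patients**

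Replace 0.42 by the plan's own target of 0.585. The mean of Z is 5.22 × 0.1 × 0.537 = 0.28 at f = 10%, and 0.56 at f = 20%. The chances of a positive test are then 4.6% and 8.1%.

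**The case against.** The strongest reply is that the requirement is already in the protocol. The synopsis, the primary objective and Sections 2.6, 6.1 and 13.1 all describe patients who progressed on the combination. The sentence in Section 3.1 concerns patients treated with a CDK4/6 inhibitor, so progression on that treatment is its natural reading. The request for records presupposes such progression: it softens the supply of paperwork and does not waive the criterion. All of this stands. A reader might infer from Section 3.1 that the protocol omits the requirement, or that still-sensitive patients were in fact randomised. The documents support neither. The first overlooks Section 6.1. The second needs prior-treatment data that the documents do not contain.

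A second reply is that the instruction in Section 4 sits under a heading for the coordinating centre's own patients, and that affiliates work from a checklist backed by source documents (Appendix F). That checklist is not in the documents and may close the gap. This limits what can be said about practice. But Section 3.1 is written for every subject, and the synopsis sends all readers to Section 3 for the full criteria.

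Third, the sentence on other prior therapies belongs to the chemotherapy exclusion and says nothing about the order of treatment. A patient who progressed on a CDK4/6 combination and later took everolimus still belongs to the intended population. I accept this, and it shapes the restricted analysis proposed below.

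Fourth, Sections 10.3 and 13.6 report that the placebo expired at the end of August 2023 and that Scenario 2 patients on treatment were unblinded. The protocol version is dated February 2024. Scenario 2 is not expressly closed, but a wording change probably reaches few or no new patients.

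**Conclusion.** This is an internal inconsistency. The section used to confirm eligibility is looser than the sections that define the population, and it makes the record of progression on the combination optional. A literal check could admit patients never shown to progress on the class.

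The size of any effect on the result is unknown. The rise from 2.5% to about 7 to 15% shows only that a modest share could matter. It rests on an assumed share of 10 to 20%, no benefit at all after true progression, and a best-case hazard ratio from CDK4/6-naive patients. With a weaker effect of 0.585 the range is about 5 to 8%. None of these figures estimates this trial's error rate, and the 80% power calculation is unaffected.

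**What to change.** Reconcile Section 3.1 with the synopsis and Section 6.1, so that progression on the CDK4/6 inhibitor combination is both required and recorded.

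Because randomisation is probably over, two further steps carry most of the value:

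- For each randomised patient, record the basis of progression from prior-treatment records: which CDK4/6 inhibitor and endocrine partner, and whether progression occurred on that combination. Do this without reference to PFS outcome by arm.
- Pre-specify in Section 13.1 a PFS sensitivity analysis limited to patients with documented progression on a CDK4/6 inhibitor combination. Do not require that combination to be the last regimen, because Sections 1.2.1 and 13.1 ask only for prior progression on it.

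The intention-to-treat analysis stays primary. The cost is a protocol edit, some record review and one extra analysis, with slightly lower precision in the restricted set.
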